## **POTENTIAL BENEFITS OF THE PROPOSED RESEARCH TO THE PARTICIPANT AND OTHERS**

### *Potential Benefits Weighed Again Risk*

*Potential Benefits Weighed Again Risk.* Participants in the study have the opportunity to: learn more about depression, co-occurring disorders, such as anxiety disorder, and its treatment, and receive an effective, guideline concordant treatment without incurring any individual costs. Furthermore, an explicit purpose of the study is to improve the accessibility and acceptability of CBT, an efficacious treatment for depression, among rural persons. Thus, participants have an improved chance to reduce their depressive symptomatology and the opportunity to share their perceptions of the intervention. Additionally, though suicide risk is a real concern in

this study, the study teams' experience researching depression suggests that asking about suicidality and having a comprehensive plan for responding to such risk holds the benefit of improved identification and treatment of persons at high risk for suicide. The potential benefits of intervening with a suicidal person are evident and represent a well-documented public health need.

The risks discussed above will all be minimized by the procedures we plan to implement as part of the data collection protocol. Burden is minimal because participants can terminate the interview whenever they begin to find it burdensome. Confidentiality risks are virtually eliminated by the special procedures adopted to separate identifying records from data files. Risks of emotional distress created by the assessment interview or intervention appear to be minimal. Nonetheless, we will include procedures to terminate assessment interviews whenever there is evidence that distress is being created. We will also have clinical back-up from study team members (e.g., [name], [name]) who are licensed clinical social workers and they can intervene if the assessment interview or intervention appears to create distress. Finally, all participants will be remunerated for each stage of their participation, totaling up to \$255. In sum, potential benefits for the research far outweigh the risks for the participants. Finally, all participants will be remunerated for each stage of their participation, totaling up to \$255. In sum, potential benefits for the research far outweigh the risks for the participants.

## DATA SAFETY AND MONITORING PLAN

For the proposed project, a number of safeguards will be implemented to ensure the safety of participants and the integrity of the data, based on guidance from the NIH Notice for Data and Safety Monitoring (OD-00-038). First, all study procedures, documents, and safety plans will be submitted and approved by the University of Michigan Medical School Institutional Review Board (MEDIRB). This will include a mechanism for reporting any adverse events to the MEDIRB and to the NIH. The UM MEDIRB reviews all adverse events reported. The study investigators will fully and promptly inform the NIH of any actions taken by the UM MEDIRB in response to adverse events.

We will establish a Data Safety Monitoring Board (DSMB) to monitor human participant protections on an ongoing basis at the University of Michigan. The DSMB is a monitoring body established in keeping with NIH guidelines for the appropriate oversight and monitoring of the conduct of clinical trials. The DSMB will convene a minimum of two times each year during the active phase of the study, to review the following: (a) research protocol and plans for data and safety monitoring, (b) adverse events and unforeseen outcomes, (c) ethical issues related to recruitment activities, (d) risk management policies and activities, and (e) intermediary data analyses. They will evaluate the progress of the proposed intervention trial through regular assessments of data quality, participant recruitment, and risk versus benefit, retention, and performance of the trial site. The DSMB will make recommendations to the IRB and study investigators concerning continuation or conclusion of the trial.

Proposed members of the DSMB include University of Michigan faculty members [name] and [name]. We will name an additional member from outside of the University to join the board. In keeping with the "NIH Policy for Data and Safety Monitoring," additional members will be included in the DSMB or consultants will be involved as necessary to interpret the data and ensure participant safety. For instance, the expertise of a biostatistician who is uninvolved with the study could potentially be needed.

Each year, the DSMB will issue a report that summarizes:

1. (1) All serious and unexpected adverse events (e.g., inpatient hospitalizations or significant worsening of clinical status) or other unanticipated problems that involve risk to study participants or others, and whether these appeared related to the study-based interventions or research assessment protocols.
2. (2) The committee's judgments regarding the assurance of the participants' safety, privacy, and confidentiality.
3. (3) Judgments as to whether research instruments have been administered appropriately while assuring participants' confidentiality.
4. (4) The committee's review of the study's progress toward recruitment goals, quality of data, treatment adherence, and participant retention/attrition rates.

5. (5) The committee's review of new research relevant to the safety of participants or the ethics of participation (for example, new therapeutic developments).
6. (6) Its recommendations as to whether risk/benefit ratios have changed to the extent that the trial should be modified or discontinued. Specific recommendations for protocol modifications will be described, with the accompanying rationale for each.

DSMB reports will be filed immediately with the IRB, as well as with the NIH Project Officer and the NIH Office for Human Research Protections (OHRP). The reports will include the dates that the committee met and the procedures used for monitoring participants' safety, confidentiality, and data integrity. The principal investigator will take responsibility for reporting any serious and unexpected adverse events in a timely fashion directly to the DSMB and IRB. Actions taken by the IRB in response to adverse event reports will be immediately reported to the DSMB and the NIMH Project Officer and OHRP office. The principal investigator recognizes the need for regular communication between the DSMB and the IRB.

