### **Aim 1: Develop and test a computer-assisted group-based cognitive behavioral therapy (CBT) for depression (Raising Our Spirits Together (ROST))**

### **Part 3: Randomized Controlled Trial (Phase I/II RCT) of ROST compared to and Enhanced Control Condition**

**Purpose.** The purpose of this project is to conduct a Phase I/II RCT of ROST, evaluating its preliminary effect on depression relative to an enhanced control condition (ECC; see below).

**Intervention Arm: Raising Our Spirits Together (ROST).** ROST is an 8-session, computer-assisted, group-based cognitive behavioral therapy (CBT) for depression that is intentionally designed for delivery by clergy in rural church settings or remotely via secure videoconference software available via the University of Michigan. ROST uses a combination of video-based educational content, text-based educational content, and a character-driven storyline to introduce core CBT concepts, including psychoeducation, behavioral activation, cognitive restructuring, and problem solving. The ROST intervention package also includes a participant workbook and intervention manual for group leaders.

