Participants randomized to ROST will complete weekly sessions that last for approximately ninety minutes (8 sessions total). ROST will either be delivered in-person at one of our partner churches, or virtually, via secure, web-based videoconferencing software available through the University of Michigan. The pastor will facilitate in-person and virtual pilot groups. Participants randomized to ROST will receive \$10 for each ROST session they attend to compensate them for travel and parking expenses.

**Clinical Backup.** We recognize ROST leaders will need clinical backup. [name] and [name], who are both licensed clinical social workers, will provide clinical backup and will be available for group leaders via phone or video conference consultation if a study participant’s condition worsens or suicidality is present. Contact between clinical backup, group leaders, and study participants will be tracked to inform ROST feasibility. Study team members providing clinical back up will complete a half-day training that includes an overview of ROST, their role, and relevant study procedures related to risk assessment and safety planning.

**Control Arm: Enhanced Control Condition (ECC).** An enhanced control condition (ECC) is an appropriate comparison condition for the RCT, given the limited treatment access in the rural target community. When participants screen positive for depression, there is an ethical obligation to provide resources and referrals. ECC participants will receive a self-help workbook that provides psychoeducation, as well as local resource guides and appropriate referrals. Ongoing risk assessment of ECC participants will occur at post-treatment (PT) and follow-up (FU) assessment timepoints. The suicide risk protocol (see Protection of Human Participants) will be followed if suicidal ideation is present.

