**In-Session Measures.** Participants randomized to ROST will complete a series of measures after each ROST sessions. The measures will be completed via REDCap online survey software. If ROST is held in person, participants will complete the online measures on site via a tablet. If ROST is held virtually, RAs will administer the online measures using REDCap online survey software distributed via email for the participants to complete after the group, while still in the Zoom room with RAs. Participants will complete weekly depression ratings (PHQ-9) to track symptoms during ROST. If participants endorse suicidal ideation on the PHQ-9 (score >0 on Question 9), they will complete the Columbia-Suicide Severity Rating Scale (C-SSRS). C-SSRS scores will be calculated via the REDCap survey software and connected to the corresponding suicide risk level (established via C-SSRS). If measures are completed onsite via table, all participants who complete the C-SSRS will be prompted by the online survey software to check in with their group leader and a Research Associate who will review their scores and risk level. If measures are completed by phone with an RA, the RAs will receive the participant's C-SSRS score and the risk level in real time. If a participant is at low risk, the Research Associate will encourage them to call the local Psychiatric Emergency Service and to discuss feelings with family members. Participants who are at low risk for suicidal ideation will continue participating in ROST sessions and their suicidal ideation will be monitored weekly until it is minimal. If a participant is at moderate or high risk for suicidal ideation, the Research Associate will immediately connect them to clinical back up – either [name] or [name] – both of whom are licensed clinical social workers. The clinical back up will assess risk and develop a safety plan with the participant and the Research Associate. After the plan is developed, it will be documented by the Research Associate who will complete a text-entry action plan via the REDCap survey. Please see the Human Subjects Protection section for a detailed description of risk levels and associated action/safety plans. Participants randomized to ROST who experience clinical deterioration over time in treatment (as indicated by an increase of 5 points or more on the PHQ-9 for participants with scores of 10 or above) will be contacted by a study team member and referred to local resources that can provide an increased level of care. Participants will also complete the Automatic Thoughts Questionnaire and the Behavioral Activation for Depression Scale at each weekly ROST session. The Group Cohesion Scale will be completed during Sessions 1, 4, and 8 and the Expectancy Rating scale will be completed during Session 3.

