
**Follow-up interviews.** All participants who completed the baseline mental health assessment interview will complete interviews at post-treatment (PT) and at 3-month follow-up (FU) timepoints. These interviews will be completed in person, over the phone, or via secure, web-based videoconferencing software available via the University of Michigan (i.e., Zoom). Research Associates will administer the same measures at post-treatment and 3 month follow-up that were assessed during the baseline interview (see Table 4). Supplemental questions will be asked to participants randomized to ROST who did not respond to the treatment or dropped out of treatment. This will allow us to gather information on intervention acceptability, feasibility, and choice points. Participants will receive \$25 for completing follow up interviews. These interviews will take about 1.5 hours to 2 hours.

**Treatment Fidelity and Group Leader Competence.** To ensure fidelity, an independent assessor (IA: Masters-level clinician with CBT experience and study-specific training) will rate leader adherence and competence using a version of the Collaborative Study Psychotherapy Rating Scale-Cognitive Therapy and the Cognitive Therapy Scale adapted for this study. All RCT sessions will be audio-recorded with participant consent and rated by the IA for treatment adherence and leader competence. [name] and [name] will review audio-recordings and competency ratings. The IA will regularly attend research meetings to discuss findings. [name] and [name] will provide weekly supervision to group leaders. [name] and [name] will review recordings for coverage of content and group leader competence, addressing any issues during weekly supervision with group leaders. We will develop a plan to incorporate missing content into the next session.

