**Table 4. Measure Administration Schedule**

Table 4. Measure Administration Schedule				
Category	Measures	Items	Timepoint(s)	Type
Screening	Patient Health Questionnaire-2 (PHQ-2)	2	Screening	PR

	6-item Mini Mental Status Exam	6	Screening	IA
Diagnosis & Symptom Scales	Patient Health Questionnaire-9  (PHQ-9)	10	BL PT FU; Sessions 1-10	PR
	MINI International Neuropsychiatric Interview v. 7 for DSM-V disorders  (MINI)	60 +	BL, PT, FU	DI
Symptom Scales	Beck Depression Inventory  (BDI)	21	BL, PT, FU	PR
	Generalized Anxiety D-7  (GAD-7)	7	BL, PT, FU	PR
Functional Impairment	Sheehan Disability Scale  (SDS)	3	BL, PT, FU	PR
	Quality of Life Enjoyment & Satisfaction Questionnaire – SF  (Q-LES-SF)	14	BL, PT, FU	PR
Mechanisms of Change	Thoughts			
	Automatic Thoughts Questionnaire  (ATQ)	30	Sessions 1-10	PR
	Dysfunctional Attitudes Scale – Short Forms  (DAS)	18	BL; PT; FU	PR
	Behaviors			
	Behavioral Activation for Depression Scale  (BADS)	25	Sessions 1-10	PR
	Environmental Reward Observation Scale  (EROS)	10	BL; PT; FU	PR
	Stigma			
	Perceived Devaluation and Discrimination Scale  (PDDS; public stigma)	12	BL, PT, FU	PR
	Internalized Stigma of Mental Illness Scale  (ISMIS; internal stigma)	29	BL, PT, FU	PR
	Social Support			
	Interpersonal Support Evaluation List -12 (ISEL-12) 	12	BL, PT, FU	PR
	Willingness to Accept Help			
	Attitudes Toward Seeking Professional Psychological Help Scale - SF 	10	BL, PT, FU	PR
	Perceived Barriers to Psychological Treatment 	24	BL, PT, FU	PR
Moderators	Religiosity			
	The Duke University Religion Index 	5	BL	PR
	Depression Severity			
	Beck Depression Inventory  (BDI)	21	BL	PR
	User Engagement			
	User Engagement Scale -Short Form	12	PT	PR
Service Use	Follow-up Mental Health Service/Medication Use Questionnaire 		FU	PR
Treatment Fidelity & Adherence	Collaborative Study Psychotherapy Rating Scale – Cognitive Therapy 	28	Sessions 1-10	IA
	Cognitive Therapy Scale 	13	Sessions 1-10	IA
	Expectancy Rating 	6	BL, Session 3	PR
	Group Cohesiveness Scale 	7	Sessions 1,5,10	PR

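### PHQ-9 worsening and suicidal ideation are looked for at up to 10 post-baseline points in ROST but at 2 in ECC, so any by-arm harm summary would be expected to show more in ROST even if the arms were identical

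*Combined protocol and SAP*

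**What the plan says.** - **ROST.** Under Part 3, "ROST is an 8-session, computer-assisted, group-based cognitive behavioral therapy (CBT) for depression". Under Procedures, In-Session Measures: "Participants will complete weekly depression ratings (PHQ-9) to track symptoms during ROST", and "If participants endorse suicidal ideation on the PHQ-9 (score >0 on Question 9), they will complete the Columbia-Suicide Severity Rating Scale (C-SSRS").
- **Both arms.** Under Follow-up interviews, everyone who completed baseline "will complete interviews at post-treatment (PT) and at 3-month follow-up (FU) timepoints".
- **ECC.** Under Control Arm: "Ongoing risk assessment of ECC participants will occur at post-treatment (PT) and follow-up (FU) assessment timepoints". No ECC assessment is scheduled during the weeks when ROST sessions run.
- **Table 4** gives the PHQ-9 schedule as "BL PT FU; Sessions 1-10", which conflicts with the 8 sessions in the text.
- **Worsening.** The Clinical Deterioration paragraph (Removing Participants from the Protocol) uses a rise of 5 points on the PHQ-9 in people scoring 10 or above. It does not name the assessment from which the rise is measured.
- **Reporting.** The Data Safety and Monitoring Plan has the DSMB summarize "All serious and unexpected adverse events (e.g., inpatient hospitalizations or significant worsening of clinical status"), state whether these appeared related to the interventions or the assessments, and recommend whether to modify or discontinue. Its remit includes "regular assessments of data quality, participant recruitment, and risk versus benefit, retention, and performance of the trial site".

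Nothing in Data Analyses or the monitoring plan limits harm summaries to the visits that both arms share, records how an event was found, or allows for the number of assessments.

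**The concern.** Whether a fluctuating score is ever seen to cross a threshold depends on how often it is measured. If one arm is measured weekly and the other is not, the count of participants with at least one detection differs by design, and the excess falls on the intervention arm. Group leaders, who are listed as a source of safety concerns, add a weekly channel that exists only in ROST.

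The trial tests a clergy-led therapy in about 42 participants per arm, so a handful of extra events is visible. An excess produced by surveillance could be read as harm in a risk-benefit judgment, and a final adverse event table by arm would carry the same artefact.

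**Working it through.** The documents state no harm rate or expected event count, so there is no figure of the plan's own to reproduce.

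**1. Post-baseline looks.** ROST: 8 + 2 = 10 (or 10 + 2 = 12 if Table 4 is followed). ECC: 2.

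**2. Direction, independent looks.** With the same probability p of a positive finding at each look, P(at least one in k looks) = 1 − (1 − p)^k. At an assumed p = 10%:
- ECC: 1 − 0.9² = 19.0%.
- ROST: 1 − 0.9¹⁰ = 65.1%, a ratio of 3.4.
- If half the sessions are attended (6 looks): 1 − 0.9⁶ = 46.9%, a ratio of 2.5.

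Over p = 5% to 20% with all sessions attended, the ratio runs from 4.1 to 2.5.

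**3. Correlated looks (relevant to item 9).** Looks on one person are not independent. In an equicorrelated latent-normal model with p = 10% per look, the figures are 40.3% against 16.8% at correlation 0.5 (ratio 2.4) and 20.5% against 13.1% at 0.9 (ratio 1.6). The ratio is 1.0 only at correlation 1, when repeated looks add no information.

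**4. PHQ-9 worsening, same course in both arms.** Assumptions, none from the documents: true mean 12; between-person SD 4; whole-number scores from 0 to 27; entry at 5 or more; improvement linear over the 8 weeks and then held; 200,000 simulated people per setting. A flag is a score of at least 10 that is at least 5 above baseline. Every session is attended and every single flag counts:

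| Improvement | Within-person SD | ROST | ECC |
|---|---|---|---|
| 2 points | 2 | 12.7% | 1.8% |
| 2 points | 2.5 | 24.3% | 5.1% |
| 2 points | 3 | 34.6% | 9.2% |
| none | 2 | 25.3% | 9.0% |
| none | 2.5 | 38.4% | 15.4% |
| none | 3 | 48.3% | 21.1% |

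At 42 per arm, SD 2.5 and 2 points: 42 × 0.243 = 10.2 against 42 × 0.051 = 2.1.

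A separate model (PHQ-9 SD 5, mean 10 or 13, reliability 0.6 to 0.9, flat course, three readings of the 5-point rule) gives ratios of 2.2 to 4.7.

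**5. Sensitivity of the SD 2.5, 2-point setting.**
- Weekly flags must hold at two consecutive looks, with PT and FU flags counted singly as in ECC: 8.4% against 5.1%, or 42 × 0.084 = 3.5 against 2.1. With no improvement the same rule gives about 20% against 15%.
- 60% attendance, single flags: 18.6% against 5.1%. At 50%: 16.8%.

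**6. Restricting the comparison to PT and FU.** Both arms then have 2 looks, so identical arms have equal expected counts, provided that acting on a weekly flag does not change later scores. If referral after a weekly flag lowered later scores by an assumed 3 points, the PT/FU figures become 1.8% in ROST against 5.1% in ECC. The bias then runs the other way.

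**The case against.** **No between-arm harm comparison is written down.** Data Analyses has no harm outcome, and the DSMB report can be read as a case listing with a relatedness judgment. No section says that the board sees counts by arm. This stands, so the point is conditional on such a summary being made. It keeps its force because the board must weigh risk against benefit and relatedness to the intervention, and a final report by arm would show the artefact.

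**The link from the PHQ-9 rule to DSMB events is inferred.** The monitoring plan gives worsening of clinical status as an example of a serious and unexpected event and does not cite the 5-point rule. That rule speaks of deterioration over time in treatment, followed by evaluation. Not every weekly spike need become a reported event. This stands, and it is why the persistent-flag figure belongs beside the single-flag one.

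**Ideation and hospitalization.** The suicide-risk section leaves adverse event status to discussion with the IRB, so ideation is not automatically a count. Hospitalizations are not found by a PHQ-9 look, and mental health service use is asked about at FU without restriction to ROST. Both limits stand.

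**Other safeguards.** The information sheet, reports by participants and family, and the safety plan for the waiting and follow-up periods serve both arms. The board also reviews the protocol, so it can know that weekly measures exist only in ROST. These narrow the gap, but none adds a scheduled look in ECC during treatment.

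**The remedy is not neutral.** Weekly flags lead to action in ROST before PT and have no ECC counterpart, so a PT/FU comparison could hide harm in ROST. This stands and shapes the fix.

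**Conclusion.** The difference in schedule is documented. Its direction holds in expectation for any finding that varies between looks, although one report with small counts could differ. The size is not settled by the documents: in the SD 2.5, 2-point setting the contrast runs from about 8% against 5% to about 24% against 5%, depending on whether weekly flags must persist.

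Three stronger readings do not follow:
- That five times the looks means about five times the events, or that about 10 against 2 participants should be expected. That result needs full attendance, assumed variances and every single-week spike counted as a reportable event.
- That the DSMB will be misled into stopping the trial. The documents do not show that it receives counts by arm, nor that each 5-point rise is reported as serious and unexpected.
- That suicidal ideation and hospitalization counts are inflated in the same way. The route to the DSMB is looser for the first, and the PHQ-9 schedule does not detect the second.

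What remains is a gap in reporting that should be closed before any counts by arm are seen.

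**What to change.** In the Data Safety and Monitoring Plan, and for the final report, state that:

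1. Every adverse event record shows how the event was found: session measure, PT or FU interview, or spontaneous report.
2. Events found only through weekly ROST measures are listed separately as ROST-only surveillance and stay fully visible to the DSMB.
3. Any ROST–ECC comparison of PHQ-9 worsening, item 9 endorsement and C-SSRS level uses PT and FU.
4. Beside that comparison stand the number of assessments per arm and the number of ROST participants referred or removed after a weekly flag.

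The cost is a few sentences and one field on the adverse event form, with no new visits or measures. The between-arm table will hold fewer events, and the PT/FU comparison is not fully neutral, which is why item 4 is needed.

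Handling of individual safety signals is unchanged. The study team must reconcile two pairs of passages that bear on these counts: whether deteriorating participants are referred (In-Session Measures) or also removed from the trial (Clinical Deterioration), and 8 sessions in the text against Sessions 1-10 in Table 4. The plan should also say from which assessment the 5-point rise is measured when events are tabulated.
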